### **Statistical Analysis Plan**

In response to reviewer's concerns, we addressed statistical concerns with this program by recruiting the services of [name]. (Associate Professor of Preventative Medicine and Epidemiology and biostatistician, Loyola University Chicago). [name] has generously agreed to serve as lead statistician of this study. He will be responsible for the statistical analyses of all collected study data. The statistical analytical sections of this revised application, including determination of subject sample size, have been substantially revised per the advice of [name].

All data will be entered in SPSS 15 for Windows (SPSS, Inc., Chicago, IL). Results will be expressed as mean  $\pm$  SEM of (n) observations. To directly test the hypothesis that a combined influence of aerobic and isokinetic strength training will enhance recovery of peripheral nerve function, measures of conduction velocity and amplitude will be analyzed by way of a 2 x 2 factorial analysis of covariance followed by a Bonferroni's multiple comparison post-hoc analysis according to the following scheme:

		Isokinetic Strength Training	
		No	Yes
Aerobic Training	No	Sedentary controls	Isokinetic strength exercise
	Yes	Aerobic exercise	Aerobic plus isokinetic strength exercise

Data collected at 12 weeks will be analyzed, using baseline measurements as a covariate. This will be repeated with the data that are collected at 24 weeks. In both analyses, primary interest will be in the combined aerobic training plus isokinetic strength training interaction. We hypothesize that patients with the combined exercise program will experience the best outcome. Although data will be collected across three time periods (baseline, 12 weeks, and 24 weeks), we have chosen to not employ a repeated measures design. There are two reasons for this: (i) the proposed study is designed to determine the combined influence of aerobic and isokinetic training on recovery of peripheral nerve function, which we believe is best achieved with a factorial design and (ii) our previous experience identified baseline differences among groups of diabetic neuropathy subjects. These group differences will go uncontrolled using a repeated measures design, but can be controlled statistically with analysis of covariance. Therefore, the aerobic plus isokinetic strength training interaction for our primary electrodiagnostic measures will be observed at 12 weeks, controlling for baseline values. This will be done again for the data collected at 24 weeks. A 2 x 2 factorial analysis of covariance also will be conducted with secondary outcome measures such as changes in aerobic capacity, peak torque, pain perception and health care use. Again, data collected both at 12 and 24 weeks will be analyzed using baseline measurements as a covariate. These analyses will allow us to observe the extent to which the secondary measures dovetail with the primary electrodiagnostic measures. In addition, primary outcomes will be correlated with secondary outcomes in order to assess the association of recovery of peripheral nerve function and quality of life. Partial correlation coefficients will be computed at 12 weeks, controlling for baseline values. This will be repeated for the data collected at 24 weeks.

**Sample Size Estimate:** The requisite sample size for the proposed study has been based upon the primary outcome measure endpoints of conduction velocity and amplitude. In our preliminary studies (see Table 2), we present data from peroneal nerve conduction velocity and amplitude for sedentary and aerobic (PoleStriding) exercise study groups. We use this information for the proposed study. However, we have not conducted strength training studies and, as such, have had to estimate values that we believe are realistic outcomes. The table below is an estimate of the conduction velocity findings for the proposed study.

		Isokinetic Strength Training	
		No	Yes
Aerobic Training	No	38 m/s	39 m/s
	Yes	39 m/s	43 m/s

Using these estimates we have computed that the effect size for the aerobic plus isokinetic strength training interaction is 0.36. From this, computations indicate that 17 subjects per group will provide 80% power with analysis of covariance to detect an effect size of that magnitude using a 0.05 alpha level. In terms of conduction amplitude, the following table is an estimate of the findings for the proposed study. Again, data from our preliminary studies are incorporated.

		Isokinetic Strength Training	
		No	Yes
Aerobic Training	No	1.9 mV	1.9 mV
	Yes	2.4 mV	4 mV

Using these estimates we have calculated the effect size for the aerobic training-by-isokinetic strength training interaction to be 0.25. Subsequently, computations indicate that greater than 20 subjects per group will be needed to provide 80% power with analysis of covariance to detect an effect size of that magnitude using a 0.05 alpha level. Given the variability in electrodiagnostic findings *between* our elderly study subjects, inherent limitations in statistical Power are unavoidable. Smaller sample sizes are calculable using *within* person changes. **However, experience gained from our previous funding cycle clearly demonstrates that some electrodiagnostic measures, such as peroneal motor amplitude responses, markedly and significantly increase with aerobic training in diabetic subjects (Table 2, Preliminary Studies).** We hypothesize a larger effect size with the addition of isokinetic strength training which will yield more Power to these analyses using a subject group size of 20. During our previous funding cycle, four of twenty-one (19%) subjects randomized to longitudinal exercise withdrew from study participation. In anticipation of a similar attrition rate, five additional subjects per group will be enrolled, totaling 100 subjects randomized to the four groups. Delays in recruiting during the last funding period have been addressed and resolved. Using the large established pool of recruits, we respectfully argue that our ability to recruit 100 subjects into this 24-week study over a 4-year period is realistic largely because: (i) the proposed time commitment is considerably less than our previously funded application (6 months vs. 18 months) and (ii) we have established a unique data base of study-qualified subjects from which to recruit.

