## Specific Objectives

The primary outcome measure of this study is recovery of peripheral nerve function in type 2 diabetic Veterans. Secondary outcome measures of exercise intervention include changes in aerobic capacity, peak torque, pain perception and health care use. Exercise-induced rehabilitation of diabetic veterans with neuropathy is an overdue concept that remains poorly studied and merits a prospective clinical investigation. Edward Hines, Jr. VA hospital will serve as a readily available resource for completing these studies.

The hypothesis of this study will be tested with the following two *Specific Objectives*:

- a. We will determine the effect of aerobic training, isokinetic strength training, or the combination of aerobic plus isokinetic strength training compared with non-exercise intervention on recovery of peripheral nerve function in age-matched type 2 diabetic Veterans with neuropathy.
  - i. Type 2 diabetic Veterans with established staged length-dependent sensorimotor polyneuropathy will be randomized to a 12 week program of exercise (aerobic, isokinetic, or the combination) or control (non-exercise) intervention. Isokinetic strength promoting leg extensions will be performed on a calibrated Biodex System 3 dynamometer. Aerobic exercise will consist of walking. Sustainability of intervention will be evaluated by repeated testing at 24 weeks. All subject groups will participate in identical biweekly diabetes-related Health Promotion Educational seminars designed to normalize participation.
  - ii. The effects of aerobic training, isokinetic strength training, or the combination of aerobic and isokinetic strength training compared with non-exercise intervention on recovery of peripheral nerve function will be statistically determined from baseline and follow-up testing using a battery of qualitative and quantitative assessments that include clinical history, physical and neurological examination, electrodiagnostic primary outcome measures, Quantitative Sensory Testing, completion of Total Neuropathy Score, visual analogue pain scale, quality of life (SF-36V Health Survey), peak torque (Biodex), peak oxygen uptake (incremental symptom-limited treadmill test) and everyday physical activity (Actical accelerometer physical activity counts).

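### The Bonferroni post-hoc step should be replaced by Holm, which is never less powerful at the same family-wise error, and its contrasts should be named

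*Combined protocol and SAP*

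**What the plan says.** The Statistical Analysis Plan specifies a 2 x 2 ANCOVA "followed by a Bonferroni's multiple comparison post-hoc analysis", and the scheme is the four-cell table of aerobic by strength training. This is the only mention of a multiplicity method. The text gives no list of contrasts and no number of tests. It also does not say whether the correction extends over nerves, over velocity and amplitude, or over the 12- and 24-week analyses.

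Three questions are put to these data:

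- **Interaction.** "In both analyses, primary interest will be in the combined aerobic training plus isokinetic strength training interaction". The Sample Size Estimate is built on this test at alpha 0.05.
- **Objective a (Specific Objectives).** The effect of each of the three programmes "compared with non-exercise intervention on recovery of peripheral nerve function". That is three contrasts with control.
- **Directional hypothesis.** "We hypothesize that patients with the combined exercise program will experience the best outcome". To support it, combined training must beat control, aerobic and strength, which is again three contrasts.

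**The concern.** A significant interaction does not show that combined training beats either component. Only contrasts between cell means can show that, and these contrasts go through the Bonferroni step. Bonferroni holds every contrast to the strictest threshold, even after others in the family have been rejected. Holm starts at that threshold and relaxes it as hypotheses are rejected, with the same family-wise guarantee. The family is also undefined. If it is every pair, aerobic versus strength is paid for although neither objective a nor the directional hypothesis needs it. At stake is missing a real advantage of combined training because of the adjustment alone.

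**Working it through.** **1. Inputs from the Sample Size Estimate.** Velocity means: control 38, strength 39, aerobic 39, combined 43 m/s; interaction effect size f = 0.36. Amplitude means: 1.9, 1.9, 2.4, 4 mV; f = 0.25. Working group size 20 (25 randomised). Alpha 0.05, taken as two-sided.

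**2. The plan's own figure.** For a 1-df interaction F test with one covariate, λ = f² × 4n and error df = 4n − 5. With f = 0.36, power is 80.9% at n = 16 and 83.2% at n = 17. The stated 17 per group is therefore reproduced to within one patient per group.

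**3. Implied SDs.** The supplied text gives no SD, so these are assumptions. From f = (interaction contrast / 4) / SD:

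- Velocity: contrast 43 − 39 − 39 + 38 = 3; SD = 0.75 / 0.36 = 2.08 m/s.
- Amplitude: contrast 4 − 2.4 − 1.9 + 1.9 = 1.6; SD = 0.4 / 0.25 = 1.6 mV.

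**4. Critical values** (20 per group, 75 df, two-sided): Bonferroni over six 2.71; Bonferroni over three 2.45; Dunnett against control 2.40; unadjusted 1.99. Holm over three contrasts uses 0.05/3, then 0.05/2, then 0.05, so its last step is at 1.99.

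**5. A check by hand for amplitude.** The standard error of a difference is 1.6 × √(2/20) = 0.506 mV. The hardest contrast is combined versus aerobic: 1.6 / 0.506 = 3.16 standard errors. Approximate power is Φ(3.16 − 2.71) = 67% at the six-pair threshold and Φ(3.16 − 1.99) = 88% at Holm's last step. Power for all three contrasts must lie somewhat below these.

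**6. Simulated power for combined to beat all three arms** (400,000 trials per row, 20 per group):

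| Outcome, SD | Six pairs: Bonferroni | Six pairs: Holm | Three contrasts: Bonferroni | Three contrasts: Holm |
|---|---|---|---|---|
| Amplitude, 1.6 mV (implied) | 64% | 70% | 73% | 86% |
| Amplitude, 1.0 mV | 99% | >99% | >99% | >99% |
| Amplitude, 2.5 mV | 16% | 20% | 23% | 39% |
| Velocity, 2.08 m/s (implied) | ~100% | ~100% | ~100% | ~100% |
| Velocity, 4 m/s | 51% | 58% | 62–63% | 78% |

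Requiring all three contrasts at an unadjusted 0.05 gives 86.4% for amplitude at 1.6 mV, hardly more than Holm over three. With 25 per group, the six-pair amplitude figures are 78% (Bonferroni) and 83% (Holm).

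**7. Contrasts with control at the implied SDs.**

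- Combined versus control, amplitude: 92.2% (Bonferroni, six), 93.4% (Holm, six), 95.3% (Bonferroni, three), 95.4% (Holm, three), 95.8% (Dunnett).
- One programme versus control, velocity: 12% (Bonferroni, six), 20% (Holm, six), 18% (Bonferroni, three), 26% (Holm, three), 20% (Dunnett).
- Aerobic versus control, amplitude: at most 10% under any of these.

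**8. Two procedures side by side, each at 0.05.** Take aerobic and combined equal and far above strength and control, which are also equal. Holm over the control contrasts then makes a false claim about strength in about 5.0% of trials. The rule that all three combined contrasts reach 0.05 makes a false claim in about 2.5%. Either error occurs in 7.3%. Pairing Dunnett with that rule reached at most 5.1% in the configurations tried.

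**The case against.** Bonferroni is valid and conservative, and using it for a post-hoc step contradicts nothing in the plan. The question on which the trial was sized loses nothing: at 20 per group, interaction power is 88.8% for velocity and 59.8% for amplitude whichever post-hoc method is chosen. At the plan's own velocity means and implied SD there is nothing to gain. Both SDs are back-solved. All of this stands and limits the size of the point.

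Two stronger readings are tempting, and the documents do not support them:

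- **That the plan commits to all six pairs and so wastes power on its questions generally.** No number of comparisons is given. If Bonferroni covers only the three contrasts with control, its critical value is 2.45 against 2.40 for Dunnett, and combined versus control on amplitude moves only from 95.3% to 95.8%. The case for Holm does not need the all-pairs reading, because Holm is at least as powerful on any family.
- **That Dunnett and an all-must-win rule are improvements at no cost.** Dunnett leaves combined versus each component untested. An all-must-win rule supports no individual claim if one contrast fails. Run beside another procedure without a stated order, it can push family-wise error above 0.05 (step 8).

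**Conclusion.** The point holds as a cheap improvement to a secondary step, not as a flaw in the primary analysis. On the same family and at the same family-wise error, Holm is never less powerful than Bonferroni. At the plan's own values the material gain is for combined training beating all three arms on amplitude: 6 percentage points over six pairs (64% to 70%), or 13 over the three relevant contrasts (73% to 86%). Naming the smaller family and using Holm together account for 64% to 86%, if six pairs were intended.

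For velocity a gain appears only if the SD is well above 2.08 m/s. The figures rest on the plan's cell means, 20 per group and the back-solved SDs. No choice of adjustment rescues the single-programme contrasts: at most 26% power for velocity and 10% for aerobic training on amplitude.

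**What to change.** In the Statistical Analysis Plan, replace Bonferroni with Holm for the post-hoc comparisons and name two families:

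1. Objective a: aerobic, strength and combined, each versus control.
2. Combined is best: combined versus control, aerobic and strength.

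Report aerobic versus strength descriptively, outside both families. State which family is tested first, or how alpha is divided. Combined versus control belongs to both, and two families each run at 0.05 are not jointly held at 0.05.

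Optionally, claim that combined is best only if all three of its contrasts favour it at two-sided 0.05. If so, state its order or alpha share relative to the first family, because side-by-side testing reached about 0.073 with Holm.

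The cost is a few sentences, with no new data and no change to the sample size. Holm only requires ranking the p-values, so the software need not change. It gives no simple simultaneous intervals; Bonferroni intervals can still be reported for description.

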- b. We will determine the effect of aerobic training, isokinetic strength training, or the combination of aerobic plus isokinetic strength training compared with non-exercise intervention on muscle tissue oxygenation in age-matched type 2 diabetic Veterans with neuropathy.

The effect of these individual interventions on muscle tissue oxygenation will be determined from baseline and follow-up by measuring limb oxygenation of the quadricep and tibialis anterior muscle groups as quantified by non-invasive infrared spectroscopy using an InSpectra™ Tissue Spectrometer.

The immediate goal of this applied study is to quantify the effects of aerobic training, isokinetic strength training, or the combination of aerobic and isokinetic strength training compared with non-exercise intervention on recovery of peripheral nerve function in the type 2 diabetic Veteran with neuropathy. Defining neural adaptive responses to individual and combined exercise interventions will allow for immediate institution of applied exercise therapy. The benefits of exercise on recovery of peripheral nerve function in diabetic patients have not been established. Exercise intervention would provide a safe achievable therapeutic option to millions of Americans affected by this disorder. A Long-term benefit of this study that extends beyond its present scope includes the application of guided exercise protocols in the prophylactic treatment of type 2 diabetic subjects with neuropathy. This single-site clinical study will provide the critical evidence required to objectively and critically define the functional significance of exercise as a rehabilitative option for the neuro-compromised diabetic Veteran.

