As part of the evaluation for such conditions, if not done within the previous six months, all subjects will have a CBC, ESR, CRP, ANA, BUN, creatinine, electrolytes, calcium, phosphorus, AST, bilirubin, alkaline phosphatase, B12, TSH, quantitative immunoglobulins, serum protein electrophoresis, and immunofixation. These studies will be performed by the Hines VA Hospital Chemical Laboratories.

**Specific Objective A: We will determine the effect of aerobic training, isokinetic strength training, or the combination of aerobic plus isokinetic strength training compared with non-exercise intervention on recovery of peripheral nerve function in age-matched type 2 diabetic Veterans with neuropathy.** Exercise intervention is firmly established as an effective strategy for the co-management of the diabetic patient. Exercise has been shown to improve maintenance of blood glucose levels and, in some cases, decreases the need for pharmacologic intervention in subjects with type 2 diabetes. Exercise intervention of 8 weeks or more statistically improves  $VO_{2\text{max}}$  in diabetic patients. Despite a clear benefit of exercise as a co-therapy for the management of diabetes, there remains a pause in the current literature regarding the effectiveness of exercise of any type for the management of established diabetic neuropathy.

**Our rationale for anticipating that exercise will improve peripheral nerve function in type 2 diabetics with established neuropathy is based on** the following published clinical data: (i) in a one-year study of lifestyle (diet and exercise) intervention, Smith *et al.* observed a modest improvement in intraepidermal nerve fiber density with decreased neuropathic pain and improved sural sensory responses (ii) improved vascular blood

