**Exercise Interventions:** Aerobic exercise will consist of treadmill walking. Isokinetic strength promoting leg extensions will be performed on a calibrated Biodex System 3 dynamometer. The use of Biodex machine is proposed as an experimental means of determining the impact isokinetic strength training has on recovery of peripheral nerve function in diabetic neuropathic veteran. Demonstrating effect with isokinetic strength training, or in combination with aerobic training, will be used as a strong rationale for implementing interventions of this type into clinical rehabilitative practice. **Subjects randomized to the combined aerobic plus isokinetic strength training** will receive isokinetic strength training followed by aerobic treadmill training so that maximal benefits can be gained from the strength program. Patients will be allowed to rest 15-30 minutes between strength and aerobic training with each session ending with a 10 minute cool-down period. Based on prior experience with exercise intervention studies, we anticipate an 80% retention rate within this intervention group. Our sample size for this group includes a 20% attrition rate to compensate for subjects unable or unwilling to complete the 24-week intervention program. Sustainability of interventions will be evaluated by repeated testing at 24 weeks. **All subject groups will participate in identical biweekly diabetes-related Health Promotion Educational seminars designed to normalize participation.**

Subjects randomized to aerobic, isokinetic, or the combination of aerobic plus isokinetic exercise group will be trained in the Physical Performance Laboratory three times weekly. A 10 minute warm-up consisting of stretching

and flexibility exercises will precede all training sessions. Exercised training duration and intensity will progress as listed in the following table:

Strength Training (maximal isokinetic muscle action; velocity of $90^{\circ} \cdot s^{-1}$ )		Aerobic Training (Walking)
Weeks 1-2	3 sets, 10 repetitions, 1 min rest between sets	25 min at 60-70% $VO_2$ peak; 5 min 71-80% $VO_2$ peak
Weeks 3-4	4 sets, 10 repetitions, 1 min rest between sets	25 min at 60-70% $VO_2$ peak; 10 min 71-80% $VO_2$ peak
Weeks 5-6	5 sets, 10 repetitions, 1 min rest between sets	25 min at 60-70% $VO_2$ peak; 15 min 71-80% $VO_2$ peak
Weeks 7-8	6 sets, 10 repetitions, 1 min rest between sets	25 min at 60-70% $VO_2$ peak; 17 min 71-80% $VO_2$ peak; 3 min 81-90% $VO_2$ peak

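### The test of primary interest is the 2 x 2 interaction, which answers neither objective a (each programme versus non-exercise) nor the claim that the combined programme is best

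*Combined protocol and SAP*

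**What the plan says.** - **Objective.** Objective a, in Specific Objectives, covers aerobic training, strength training and "the combination of aerobic plus isokinetic strength training compared with non-exercise intervention on recovery of peripheral nerve function". The immediate goal in the same section is to "quantify the effects of aerobic training, isokinetic strength training, or the combination of aerobic and isokinetic strength training compared with non-exercise intervention". Research Design and Methods repeats the comparison under Specific Objective A.
- **Expected result.** The Statistical Analysis Plan states: "We hypothesize that patients with the combined exercise program will experience the best outcome".
- **Primary test.** For the 12-week and 24-week data alike: "In both analyses, primary interest will be in the combined aerobic training plus isokinetic strength training interaction". One reason given for the factorial layout is that "the proposed study is designed to determine the combined influence of aerobic and isokinetic training on recovery of peripheral nerve function".
- **Power.** The Sample Size Estimate gives an effect size of 0.36 for conduction velocity (17 per group for 80% power) and 0.25 for amplitude (more than 20 per group). Both are described as interaction effects.
- **Group comparisons.** Velocity and amplitude are to be analysed by "2 x 2 factorial analysis of covariance followed by a Bonferroni's multiple comparison post-hoc analysis". The pairs, their number and any dependence on the interaction are not given. The Conventional Care section says that control will be compared with the exercised groups, and the section on stopping and intention to treat says that covariance analysis will compare the groups. Neither names contrasts. Main effects are not mentioned, and no contrast has a stated power.

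**The concern.** The objective and the primary test ask different questions. Objective a asks whether a programme is better than no exercise. The interaction asks whether the combined gain exceeds the sum of the two single gains. If the two modes each help and their benefits simply add, objective a is met and there is no interaction to find.

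The use planned for the result is also about effect. Under Exercise Interventions: "Demonstrating effect with isokinetic strength training, or in combination with aerobic training, will be used as a strong rationale" for bringing such training into clinical practice. If the headline analysis is a null interaction, a trial in which exercise worked could be reported as showing nothing of primary interest. The comparison with non-exercise would rest on a post-hoc step whose family is not defined.

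**Working it through.** **1. What the interaction measures.** I = combined - aerobic - strength + control. No standard deviation is needed for this step.

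| Means in m/s (control, strength, aerobic, combined) | I | Programmes versus control |
|---|---|---|
| Plan: 38, 39, 39, 43 | 43 - 39 - 39 + 38 = 3 | all better, combined best |
| Additive: 38, 39, 39, 40 | 40 - 39 - 39 + 38 = 0 | all better, combined best |
| Reversed: 40, 38, 38, 39 | 39 - 38 - 38 + 40 = 3 | all worse |

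A non-zero interaction is therefore neither necessary nor sufficient for objective a or for a best combined arm.

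**2. Reproducing the plan's sample size.** The documents supplied give no SD and do not name the effect-size metric. Assume Cohen's f for a 1-df interaction, f = |I| / (4 SD).

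- Velocity: SD = 3 / (4 x 0.36) = 2.08 m/s.
- Amplitude: I = 4 - 2.4 - 1.9 + 1.9 = 1.6 mV, so SD = 1.6 / (4 x 0.25) = 1.6 mV.

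With noncentral t, two-sided 0.05 and df = 4n - 5, f = 0.36 gives 80.9% power at 16 per group and 83.2% at 17, close to the plan's 17. A 3-df overall test would need 23. The stated velocity power is thus consistent with an interaction calculation. For f = 0.25 the same formula needs 32 per group; the plan's figure of more than 20 is only a lower bound.

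**3. Standard errors at 20 evaluable per group.** Interaction: SD x sqrt(4/n). Pair: SD x sqrt(2/n). For velocity these are 0.93 and 0.66 m/s; for amplitude, 0.72 and 0.51 mV.

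**4. Power in the additive velocity case** (combined minus control = 2 m/s):

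| Test | Power |
|---|---|
| Interaction (I = 0) | 5% |
| Each main effect (1 m/s) | 56% |
| Combined versus control, alpha 0.05 | 85% |
| Same, alpha split over two endpoints (0.025) | 77% |
| Same, one of three comparisons with control (0.05/3) | 72% |
| Same, one of all six pairs (0.05/6) | 63% |

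At alpha 0.05 the 85% becomes 99% for SD 1.5 and 55% for SD 3. With 25 per group the 85%, 72% and 63% become 92%, 83% and 76%.

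**5. Power on the plan's own means, 20 per group.**

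- Velocity: interaction 89%; combined versus control (5 m/s) over 99%.
- Amplitude: interaction 60%; combined versus control (2.1 mV) 98% at 0.05, 95% over three comparisons and 92% over six. At SD 2.5 mV the last three are 75%, 58% and 48%.
- Single mode versus control, unadjusted: 32% for 1 m/s and 16% for 0.5 mV. The planned strength-versus-control amplitude difference is 0.

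**6. Do main effects fill the gap?** Only if the modes add. On the plan's amplitude means the strength main effect is [(1.9 - 1.9) + (4 - 2.4)] / 2 = 0.8 mV, although strength alone differs from control by 0.

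**The case against.** The choice of the interaction looks deliberate. The plan speaks of a combined influence, gives that as a reason for the factorial design, and assumes more-than-additive means for both endpoints. If synergy is the scientific question, the interaction is the right test of it. That stands, but objective a, the immediate goal and the best-outcome hypothesis are then worded for a different question.

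A reader might infer that the comparisons with control have no place in the plan. The documents do not support that: the Bonferroni step belongs to the analysis of the primary endpoints, and two other sections promise group comparisons. What is missing is their list, priority and power.

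A reader might also infer that a null interaction would make the trial formally negative. The plan states a primary interest but no success rule, and does not make the post-hoc step depend on the interaction.

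Nor does the plan lack power for combined versus control on its own means; under the SDs derived above, the existing post-hoc route would deliver that comparison. The loss in the additive case depends on means chosen for illustration, and six pairs is the largest family possible, not one the plan specifies.

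**Conclusion.** The mismatch holds as written. Primary interest and all stated power go to a contrast that can be null when objective a is met, and positive when every programme is worse than control. That conclusion is algebra and does not depend on any SD.

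The size does depend on assumptions: that 0.36 and 0.25 are Cohen's f, and that the SDs derived from them apply. If those effect sizes do not already allow for baseline adjustment, all powers rise, the interaction's included (except where the true interaction is zero). On this reading the additive velocity case leaves 5% power for the interaction, against 63% to 85% for combined versus control, depending on how alpha is shared. On the plan's own amplitude means the figures are 60% against 92% to 98%.

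Changing the primary contrast does not rescue everything. Single-mode comparisons remain weak. If amplitude gains merely add (1.9, 1.9, 2.4, 2.4 mV), combined versus control has 16% power and the aerobic main effect 28%. This should be fixed before analysis.

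**What to change.** Reconcile the objective with the primary test in one of two ways.

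1. **If the question is effect versus non-exercise.** Keep the four-arm ANCOVA and make a named comparison with control primary; combined versus control is the one with adequate power on the plan's means.
   - Name the endpoint and time point, say how alpha is shared between velocity and amplitude, and restate power with the SD used.
   - List aerobic versus control and strength versus control as adjusted secondary contrasts (for example Holm over the two), and state that their power is low.
   - Require combined to beat both single modes before claiming it is best. Combined versus control alone cannot show that strength adds to aerobic training.
   - Report both main effects and the interaction with 95% confidence intervals.
2. **If the question is synergy.** Keep the interaction primary, and restate the hypothesis and objective a as more-than-additive benefit. Say that a null interaction will not be read as no effect of exercise, and list the post-hoc contrasts and their number.

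The cost is wording and, under the first option, a restated power statement; the design, data collection and 100 subjects do not change. Under the first option synergy becomes secondary and the single-mode contrasts stay low-powered. Under the second the stated objective narrows.
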